6.9. Concomitant Therapy

Medications will be classified into anatomical therapeutic chemical (ATC) drug classes using the latest version of the World Health Organization (WHO) drug dictionary.

Prior medications are those medications that start and stop prior to the date of first dose of study treatment in Period 1.

Concomitant medications are those medications:

- that start before the administration of first dose of study treatment in Period 1 and continue into the treatment period. This will be considered as **current** medication.
- that start on or after the first dose of study treatment in Period 1. Note that the medication will be assigned to the treatment period in which they are taken. For example, if a subject is receiving medication during Period 1 and has a stop date during Period 2, the same medication will be counted in Period 1 and Period 2 summaries.

Prior medications will be presented by ATC class and preferred term (PT) by treatment group for the ITT Population. Reasons for discontinuing previous CD therapy will be reviewed.

Concomitant medications considered current will be presented similarly by ATC class and PT.

Concomitant medications not considered current will be summarized separately for the following:

1. CD medication (including corticosteroids)
2. remaining medications (excluding CD medications)

The summaries will present the number and percentage of subjects taking concomitant medication by ATC class and PT for Period 1 (ITT population), Period 2 (EHO Group 2), Period 3 (EHO Group 3), and Follow-Up (ITT population).

Visual techniques will be used to examine subjects' use of corticosteroid in the context of treatment group, treatment start and stop dates, medication start and stop dates, and dose.

6.10. Efficacy Analyses

The efficacy endpoints are defined by time point and outcome measure in [Table AMAG.6.6](#). In addition, changes in Crohn's Disease Activity Index (CDAI) from baseline will be evaluated as exploratory analyses.

Table AMAG.6.6. Efficacy Endpoints

	Response	Remission	Durability
SES-CD	Weeks 12 ^a , 52 ^b	Weeks 12 ^b , 52 ^b	Week 52 ^b (Response, Remission)
PRO	Weeks 12 ^c , 52 ^c	Weeks 12 ^b , 52 ^b	Week 52 ^c (Response, Remission)
PRO2	Weeks 12 ^c , 52 ^c	Weeks 12 ^c , 52 ^c	Week 52 ^c (Response, Remission)
PRO1		Weeks 12 ^c , 52 ^c	
Composite ^d		Weeks 12 ^c , 52 ^c	Week 52 ^c
Composite ^e		Weeks 12 ^c , 52 ^c	Week 52 ^c

Abbreviations: PRO = patient-reported outcomes; SES-CD = Simple Endoscopic Score for Crohn's Disease.

a Primary Endpoint

b Secondary Endpoints

c Exploratory Endpoints

d Endoscopic Remission and PRO Remission

e Endoscopic Response and PRO Remission

6.10.1. Primary Outcome and Methodology

The primary outcome is stated in [Table AMAG.6.6](#) and its derivations/analyses are described in [Table AMAG.6.7](#) and [Table AMAG.6.8](#).

6.10.2. Secondary Efficacy Analyses

The secondary outcomes are stated in [Table AMAG.6.6](#) and their derivations/analyses are described in [Table AMAG.6.7](#) and [Table AMAG.6.8](#).

6.10.3. Exploratory Efficacy Analyses

The exploratory outcomes are stated in [Table AMAG.6.6](#) and their derivations/analyses are described in [Table AMAG.6.7](#) and [Table AMAG.6.8](#).

Table AMAG.6.7. Description and Derivation of Efficacy Endpoints

Measure	Description / Timing	Variable	Derivation / Comment
SES-CD	
SES-CD is based on 4 endoscopic variables (presence and size of ulcers, proportion of surface covered by ulcers, proportion of surface affected by disease, and presence and severity of stenosis).
 
The 4 endoscopic variables are scored from 0 to 3 in each of 5 bowel segments (ileum; right, transverse, and left colon; and rectum): presence and size of ulcers (none = score 0; diameter 0.1–0.5 cm = score 1; 0.5–2 cm = score 2; >2 cm = score 3); extent of ulcerated surface (none = 0; <10% = 1; 10–30% = 2; >30% = 3); extent of affected surface (none = 0; <50% = 1; 50–75% = 2; >75% = 3); and presence and type of narrowings (none=0; single, can be passed=1; multiple, can be passed=2; cannot be passed=3).
 
Complete details of the calculation of the SES-CD are given in Appendix 2. Higher SES-CD scores indicate more severe disease.
 
SES-CD scores are obtained at Weeks 0, 12, and 52.
	Endoscopic Response	
Endoscopic response at Week x is defined as a 50% reduction in SES-CD at Week X when compared with baseline.
 
Endpoints:
 
 • Proportion of subjects with endoscopic responses at Week 12 • Proportion of subjects with endoscopic responses at Week 52
		Endoscopic Remission	
Endoscopic remission at Week x is defined as an SES-CD of <4 ileal-colonic or <2 for isolated ileal disease, and no subscore >1 at Week x.
 
Endpoints:
 
 • Proportion of subjects with endoscopic remission at Week 12 • Proportion of subjects with endoscopic remission at Week 52
		Durability of Endoscopic Response	
Endpoint: Proportion of subjects with endoscopic response at both Weeks 12 and 52 (ie, of those subjects who achieved an endoscopic response at Week 12, the proportion who maintained an endoscopic response at Week 52).

		Durability of Endoscopic Remission	
Endpoint: Proportion of subjects with endoscopic remission at both Weeks 12 and 52 (ie, of those subjects who achieved an endoscopic remission at Week 12, the proportion who maintained an endoscopic remission at Week 52).

Description and Derivation of Efficacy Endpoints

Measure	Description / Timing	Variable	Derivation / Comment
CDAI	
The CDAI is an 8-item disease activity measure comprised of 3 patient-reported and 5 physician-reported/laboratory items. Subject responses are summed over a 7-day period and subsequently weighted, yielding a total score range of 0-600 points. For all endpoints derived using CDAI in this table, 7 days of subject-reported data within a 12-day period prior to a visit will be utilized to calculate scores. Data will be excluded from score calculations when collected on day(s) of colonoscopy prep, day of colonoscopy procedure, and 2 days after colonoscopy procedure.
 
If after excluding these values 4 days of data are not available, the value will be set to missing. CDAI data is collected at every visit during the Screening through Follow-Up Periods visits.
	PRO Remission	
PRO remission is defined as SF \leq2.5 and AP \leq1 and no worse than baseline at Week x.
 
PRO remission = (7 day average of SF) \leq2.5 and no worse than baseline and (7 day average of AP score) \leq1 and no worse than baseline
 
SF captures the number of liquid or very soft stools.
 
AP score is classified as 0=none, 1=mild, 2=moderate, 3=severe.
 
Endpoints:
 
 • Proportion of subjects with PRO remission at Week 12 • Proportion of subjects with PRO remission at Week 52
		PRO Response	
PRO response is defined as a decrease of at least 30% in either SF or AP and neither of them worse than baseline
 
Endpoints:
 
 • Proportion of subjects with PRO response at Week 12 • Proportion of subjects with PRO response at Week 52
		Durability of PRO Remission	
 • Endpoint: Proportion of subjects with PRO remission at both Weeks 12 and 52 (ie, of those subjects who achieved a PRO remission at Week 12, the proportion who maintained a PRO remission at Week 52).
		Durability of PRO Response	
 • Endpoint: Proportion of subjects with PRO response at both Weeks 12 and 52 (ie, of those subjects who achieved a PRO response at Week 12, the proportion who maintained a PRO response at Week 52).
		PRO Remission in PRO Responders	
Endpoint: Proportion of subjects with PRO remission at Week 52 and PRO response at Week 12 (ie, of those subjects who achieved a PRO response at Week 12, the proportion who achieved a PRO remission at Week 52).

Description and Derivation of Efficacy Endpoints

Measure	Description / Timing	Variable	Derivation / Comment
		PRO2 Response	PRO2 is a 2-item index comprised of the SF and AP items from the CDAI (weighted). The total PRO2 is comprised of the average daily scores over 7 days, weighted using the CDAI multiplication factors for SF and AP items. (See Appendix 6 for complete details on the CDAI form.) PRO2 = (7 day average of SF)*2 + (7 day average of AP score)*5 Proportion of subjects with PRO2 reduction of at least 5 points at Week x compared with baseline. Endpoints: 
 • Proportion of subjects with PRO2 response at Week 12 • Proportion of subjects with PRO2 response at Week 52
		PRO2 Remission	See PRO2 calculations above. Proportion of subjects with PRO2 <8 at Week x . Endpoints: 
 • Proportion of subjects with PRO2 remission at Week 12 • Proportion of subjects with PRO2 remission at Week 52
		Durability of PRO2 Response	Endpoint: Proportion of subjects with PRO2 response at both Weeks 12 and 52 (ie, of those subjects who achieved a PRO2 response at Week 12, the proportion who maintained a PRO2 response at Week 52).
		Durability of PRO2 Remission	Endpoint: Proportion of subjects with PRO2 remission at both Weeks 12 and 52 (ie, of those subjects who achieved a PRO2 remission at Week 12, the proportion who maintained a PRO2 remission at Week 52).
		PRO1 Remission	PRO1 remission is defined as SF ≤ 1.5 and AP ≤ 1 and no worse than baseline for both SF and AP at Week x . PRO remission = (7 day average of SF) ≤ 2.5 and no worse than baseline and (7 day average of AP score) ≤ 1 and no worse than baseline. Endpoints: 
 • Proportion of subjects with PRO1 remission at Week 12 • Proportion of subjects with PRO1 remission at Week 52

Description and Derivation of Efficacy Endpoints

Measure	Description / Timing	Variable	Derivation / Comment
		CDAI Total Score	The derivation is based on the CDAI questionnaire in Appendix 6 . It also utilizes the standard weights table in that section. Endpoint : Changes from baseline.
		CDAI Remission	See CDAI Total Score calculations above. Proportion of subjects with CDAI Total Score <150 at Week x. Endpoints: 
 • Proportion of subjects with CDAI remission at Week 12 • Proportion of subjects with CDAI remission at Week 52
		CDAI Response	See CDAI Total Score calculations above. Proportion of subjects achieving a CDAI reduction of ≥ 100 from baseline or CDAI <150 at Week x. Endpoints: 
 • Proportion of subjects with CDAI response at Week 12 • Proportion of subjects with CDAI response at Week 52
		CDAI Remission in CDAI Responders	Endpoints: 
 • Among CDAI responders at Week 12, the proportion of subjects with CDAI remission at Week 52.
Composite Endoscopic and PRO Remissions	Endoscopic remission: See SES-CD section above. PRO remission: See CDAI section above.	Composite of Endoscopic and PRO Remissions	Proportion of subjects achieving both endoscopic and PRO remissions at Week x. Endpoints : 
 • Proportion of subjects achieving both endoscopic and PRO remissions at Week 12 • Proportion of subjects achieving both endoscopic and PRO remissions at Week 52
		Durability of Composite Endoscopic and PRO Remissions	Endpoint : Proportion of subjects achieving both endoscopic and PRO remissions at Week 52 who also had both endoscopic and PRO remissions at Week 12 (that is, of those subjects who achieved both endoscopic and PRO remissions at Week 12, the proportion who maintained both endoscopic and PRO remissions at Week 52).

Description and Derivation of Efficacy Endpoints

Measure	Description / Timing	Variable	Derivation / Comment
Composite Endoscopic Response and PRO Remission	Endoscopic response: See SES-CD section above. PRO remission: See CDAI section above.	Composite of Endoscopic Response and PRO Remission	Proportion of subjects achieving both endoscopic response and PRO remission at Week x. Endpoints: 
 • Proportion of subjects achieving both endoscopic response and PRO remission at Week 12 • Proportion of subjects achieving both endoscopic and PRO remissions at Week 52
		Durability of Composite Endoscopic Response and PRO Remission	Endpoint: Proportion of subjects achieving both endoscopic response and PRO remission at Week 52 who also had both endoscopic response and PRO remission at Week 12 (that is, of those subjects who achieved both endoscopic response and PRO remission at Week 12, the proportion who maintained both endoscopic response and PRO remission at Week 52).

Abbreviations: AP = abdominal pain; CD = Crohn’s disease; CDAI = Crohn’s Disease Activity Index; PRO = patient-reported outcomes; SES-CD = Simple Endoscopic Score for Crohn’s Disease; SF = stool frequency.

Table AMAG.6.8 describes the analysis methods, population, and time points/associated study periods for each analysis.

Table AMAG.6.8. Description of Efficacy Analyses

Measure	Variable	Analysis Method (Section 6.1.6)	Population (Table AMAG.6.1)	Time Point
SES-CD	Endoscopic Response	Primary Analysis: Logistic regression analysis with NRI	ITT Population	Week 12
		Secondary Analysis: CMH with NRI	ITT Population	Week 12
		Descriptive Statistics with NRI	EHO Group 2	All scheduled visits through Week 52
	Endoscopic Remission	Primary Analysis: Logistic regression analysis with NRI	ITT Population	Week 12
		Secondary Analysis: CMH with NRI	ITT Population	Week 12
		Descriptive Statistics with NRI	EHO Group 2	All scheduled visits through Week 52
	Durability of Endoscopic Response	Descriptive Statistics with NRI	EHO Group 2	Week 52
Durability of Endoscopic Remission	Descriptive Statistics with NRI	EHO Group 2	Week 52	
CDAI	PRO Remission	Primary Analysis: Logistic regression analysis with NRI	ITT Population	Week 12
		Secondary Analysis: CMH with NRI	ITT Population	Week 12
		Descriptive Statistics with NRI	EHO Group 2, EHO Group 3	All scheduled visits through Week 120 (where applicable)
	PRO Response	Primary Analysis: Logistic regression analysis with NRI	ITT Population	Week 12
		Secondary Analysis: CMH with NRI	ITT Population	Week 12
		Descriptive Statistics with NRI	EHO Group 2, EHO Group 3	All scheduled visits through Week 120 (where applicable)
	Durability of PRO Remission	Descriptive Statistics with NRI	EHO Group 2	Week 52
	Durability of PRO Response	Descriptive Statistics with NRI	EHO Group 2	Week 52
	PRO Remission in PRO Responders	Descriptive Statistics with NRI	EHO Group 2	Week 52
	PRO2 Response	Primary Analysis: Logistic regression analysis with NRI	ITT Population	Week 12

Description of Efficacy Analyses

Measure	Variable	Analysis Method (Section 6.1.6)	Population (Table AMAG.6.1)	Time Point
		Secondary Analysis: CMH with NRI	ITT Population	Week 12
		Descriptive Statistics with NRI	EHO Group 2, EHO Group 3	All scheduled visits through Week 120 (where applicable)
	PRO2 Remission	Primary Analysis: Logistic regression analysis with NRI	ITT Population	Week 12
		Secondary Analysis: CMH with NRI	ITT Population	Week 12
		Descriptive Statistics with NRI	EHO Group 2, EHO Group 3	All scheduled visits through Week 120 (where applicable)
	Durability of PRO2 Response	Descriptive Statistics with NRI	EHO Group 2	Week 52
	Durability of PRO2 Remission	Descriptive Statistics with NRI	EHO Group 2	Week 52
	PRO1 Remission	Primary Analysis: Logistic regression analysis with NRI	ITT Population	Week 12
		Secondary Analysis: CMH with NRI	ITT Population	Week 12
		Descriptive Statistics with NRI	EHO Group 2, EHO Group 3	All scheduled visits through Week 120 (where applicable)
	CDAI Total Score - change from baseline	Primary Analysis: MMRM	ITT Population	Week 12
		Sensitivity Analysis: ANCOVA (mBOCF)	ITT Population	Week 12
		Descriptive Statistics	EHO Group 2, EHO Group 3	All scheduled visits through Week 120 (where applicable)
	CDAI Remission	Primary Analysis: Logistic regression analysis with NRI	ITT Population	Week 12
		Descriptive Statistics with NRI	EHO Group 2, EHO Group 3	All scheduled visits through Week 120 (where applicable)
	CDAI Response	Primary Analysis: Logistic regression analysis with NRI	ITT Population	Week 12
		Descriptive Statistics with NRI	EHO Group 2, EHO Group 3	All scheduled visits through Week 120 (where applicable)
	CDAI Remission in CDAI Responders	Descriptive Statistics with NRI	EHO Group 2	Week 52

Description of Efficacy Analyses

Measure	Variable	Analysis Method (Section 6.1.6)	Population (Table AMAG.6.1)	Time Point
Composite endoscopic and PRO remissions	Composite of endoscopic and PRO remissions	Primary Analysis: Logistic regression analysis with NRI	ITT Population	Week 12
		Secondary Analysis: CMH with NRI	ITT Population	Week 12
		Descriptive Statistics with NRI	EHO Group 2	All scheduled visits through Week 52
	Durability of composite endoscopic and PRO remissions	Descriptive Statistics with NRI	EHO Group 2	Week 52
Composite endoscopic response and PRO remission	Composite of endoscopic response and PRO remission	Primary Analysis: Logistic regression analysis with NRI	ITT Population	Week 12
		Secondary Analysis: CMH with NRI	ITT Population	Week 12
		Descriptive Statistics with NRI	EHO Group 2	All scheduled visits through Week 52
	Durability of composite endoscopic response and PRO remission	Descriptive Statistics with NRI	EHO Group 2	Week 52

Abbreviations: CDAI = Crohn’s Disease Activity Index; CMH = Cochran-Mantel-Haenszel; EHO = efficacy and health outcomes; ITT = intent-to-treat; NRI = non-responder imputation; PRO = patient-reported outcomes; SES-CD = Simple Endoscopic Score for Crohn’s Disease.

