9.1.2. Secondary Efficacy Assessments

Secondary efficacy assessments will include an assessment of the SES-CD score using centrally read endoscopy at Weeks 12 and 52, and an assessment of SF and AP at Weeks 12 and 52, using patient-reported data recorded in the patient diary, as detailed below. Changes in health outcome measures/quality-of-life measures from baseline to Weeks 12 and 52, and the PK properties of LY3074828 will also be assessed. Effects on safety parameters will also be assessed (see Section 9.5).

- Endoscopic remission is defined as an SES-CD score of <4 for ileal-colonic disease or <2 for isolated ileal disease, and no subscore >1 .
- PRO scores will be determined as an average of 7 days of data recorded by the subject within a 12-day period prior to a specified visit. Fewer than 4 days of data within a 12-day period prior to a specified visit will constitute a missing data score. Data will be excluded from score calculation when collected on day(s) of colonoscopy prep, day of colonoscopy procedure, and 2 days after colonoscopy procedure. PRO remission is defined as having an average daily AP score ≤ 1 and an average daily SF ≤ 2.5 (absolute number of liquid or very soft stools defined using the Bristol Stool Scale Category 6 or 7 [Lewis and Heaton 1997], that is, liquid or watery stools).

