10.3.3.2. Secondary Efficacy Analyses

The secondary efficacy endpoints of the trial are:

- To evaluate the efficacy of treatment with LY3074828 on endoscopic response at Week 52 (defined as 50% reduction from baseline in SES-CD Score).
- To evaluate the efficacy of treatment with LY3074828 on endoscopic remission at Weeks 12 and 52 (defined as a SES-CD score of <4 ileal-colonic disease or <2 for isolated ileal disease, and no subscore >1).
- To evaluate the efficacy of treatment with LY3074828 on PRO remission at Weeks 12 and 52 (defined as SF \leq 2.5 and AP \leq 1).

For endoscopic remission and PRO remission, subjects who do not achieve remission or who do not reach the assessment time point (Week 12 or 52) will be considered to be non-remitters for that particular endpoint at that time point and later time points if applicable.

Details of the NRI are provided in Section 10.3.1.2.

Details of the analysis methods that will be utilized are provided in Section 10.3.1.

Additional analyses of the secondary efficacy endpoints may be considered and will be fully detailed in the SAP.

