LY+FUP	All LY3074828 (Lilly study drug) data for Periods 1-3 plus all Follow-Up combined
mBOCF	modified baseline observation carried forward
CCI	
MedDRA	Medical Dictionary for Regulatory Activities
CCI	
MMRM	mixed model for repeated measures
NAb	neutralizing antibody
Nab+	NAb positive

CCI	
NRI	non-responder imputation
NRS	numeric rating scale
OI	opportunistic infection
PD	pharmacodynamics
PGRC	Patient's Global Rating of Change
PGRS	Patient's Global Rating of Severity
PK	pharmacokinetics
PT	preferred term
PRO	patient-reported outcomes: a 2-item index comprised of the SF and AP items from the CDAI (unweighted)
PRO2	patient-reported outcomes-2: a 2-item index comprised of the SF and AP items from the CDAI (weighted)
Q4W	every 4 weeks
QIDS-SR16	Quick Inventory of Depressive Symptomatology–Self Report (16 Items)
REML	restricted maximum likelihood
RHI	Robarts Histopathology Index
SAE	serious adverse event
SAP	statistical analysis plan
SC	subcutaneous
SD	standard deviation
SES-CD	Simple Endoscopic Score for Crohn's Disease
SF	stool frequency
SF-36	36-Item Short Form Health Survey
SI	International System of Units
SMQ	standardized MedDRA query
SOC	system organ class
TE ADA-	treatment-emergent ADA negative

TE ADA+	treatment-emergent ADA positive
TEAE	treatment-emergent adverse event
ULN	upper limit of normal
US	United States

3. Revision History

SAP Version 1 was approved prior to the first permanent data transfer.

SAP Version 2 was approved prior to first unblinding. The overall changes and rationale for the changes incorporated in Version 2 are as follows:

- Reflected protocol amendment (a).
- Further defined subject populations, study periods, and baseline/postbaseline for analyses.
- Added exploratory endpoints not specified in protocol based on data from new publications.

4. Study Objectives

Table AMAG.4.1 shows the objectives and endpoints of the study as noted in the protocol. Further details on the endpoints, including derivations, are described in the corresponding section of this SAP.

Table AMAG.4.1. Objectives and Endpoints

Objectives	Endpoints
Primary	
To test the hypothesis that treatment with LY3074828 is superior to placebo in the proportion of subjects with endoscopic response at Week 12 , defined as 50% reduction from baseline in SES-CD	Proportion of subjects achieving endoscopic response at Week 12
Secondary	

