To evaluate the safety and tolerability of treatment with LY3074828	AEs and discontinuation rates; mean change vital signs; laboratory values
To evaluate the effect of LY3074828 on the proportion of subjects with endoscopic response at Week 52 , defined as 50% reduction from baseline in SES-CD	Proportion of subjects achieving endoscopic response at Week 52
To evaluate the efficacy of treatment with LY3074828 as superior to placebo in endoscopic remission (defined as an SES-CD of <4 ileal-colonic or <2 for isolated ileal disease, and no subscore >1) at Week 12	Proportion of subjects achieving endoscopic remission at Week 12
To evaluate the effect of LY3074828 on the proportion of subjects with endoscopic remission (defined as an SES-CD of <4 ileal-colonic or <2 for isolated ileal disease, and no subscore >1) at Week 52	Proportion of subjects achieving endoscopic remission at Week 52
To evaluate the efficacy of treatment with LY3074828 as superior to placebo in PRO remission (defined as SF \leq 2.5 and AP \leq 1) at Week 12	Proportion of subjects achieving PRO remission at Week 12
To evaluate the effect of LY3074828 on the proportion of subjects with PRO remission (defined as SF \leq 2.5 and AP \leq 1) at Week 52	Proportion of subjects achieving PRO remission at Week 52
To evaluate the effect of LY3074828 on health outcomes/quality-of-life measures (including PGRS score, PGRC score, IBDQ score, SF-36 score, and FACIT-Fatigue) at Weeks 12 and 52	The mean change from baseline for PGRS score, IBDQ score, FACIT-Fatigue, and SF-36, and the mean PGRC at Weeks 12 and 52
To characterize the PK of LY3074828	Clearance and volume of distribution
Tertiary/Exploratory	
To evaluate the efficacy of treatment with LY3074828 as superior to placebo in PRO2 response (defined as a PRO2 reduction of \geq 5 points) at Week 12	Proportion of subjects achieving PRO2 response at Week 12
To evaluate the effect of LY3074828 on the proportion of subjects with PRO2 response (defined as a PRO2 reduction of \geq 5 points) at Week 52	Proportion of subjects achieving PRO2 response at Week 52

Objectives and Endpoints

Objectives	Endpoints
To evaluate the efficacy of treatment with LY3074828 as superior to placebo in PRO2 remission (defined as a PRO2 <8) at Week 12	Proportion of subjects achieving PRO2 remission at Week 12

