To evaluate the elimination of neutrophils from the mucosa by histopathology at Week 52.	Absence of lamina propria and epithelial neutrophils at Week 52 assessed by 
 GHAS RHI
Exploratory (not in protocol)	
To evaluate the efficacy of treatment with LY3074828 as superior to placebo in PRO response (defined as 30% reduction from baseline in AP or SF with neither worse than baseline) at Week 12	Proportion of subjects achieving PRO response at Week 12.
To evaluate the efficacy of treatment with LY3074828 as superior to placebo in PRO response (defined as 30% reduction from baseline in AP or SF with neither worse than baseline) at Week 52	Proportion of subjects achieving PRO response at Week 52.
To evaluate the effect of LY3074828 on durability of PRO response at Week 52	Proportion of subjects achieving PRO response at Week 52 who also had PRO response at Week 12.
To evaluate the effect of LY3074828 on durability of PRO remission at Week 52	Proportion of subjects achieving PRO remission at Week 52 who also had PRO remission at Week 12.
To evaluate the effect of LY3074828 on PRO remission at Week 52 among PRO responders at Week 12	Proportion of subjects achieving PRO remission at Week 52 out of those patients who had PRO response at Week 12.
To evaluate the efficacy of treatment with LY3074828 as superior to placebo in the composite of endoscopic response and PRO remission at Week 12	Proportion of subjects achieving both endoscopic response and PRO remission at Week 12
To evaluate the effect of LY3074828 on the proportion of subjects with the composite of endoscopic response and PRO remission at Week 52	Proportion of subjects achieving both endoscopic and PRO remission at Week 52

Objectives and Endpoints

Objectives	Endpoints
To evaluate the effect of LY3074828 on durability of the composite endoscopic response and PRO remission at Week 52	Proportion of subjects achieving both endoscopic response and PRO remission at Week 52 out of the patients with endoscopic response and PRO remission at Week 12
To evaluate the efficacy of treatment with LY3074828 as superior to placebo in PRO1 remission (defined as SF \leq 1.5 and AP \leq 1 and no worse than baseline) at Week 12	Proportion of subjects achieving PRO1 remission at Week 12.
To evaluate the effect of LY3074828 on the proportion of subjects with PRO1 remission at Week 52	Proportion of subjects achieving PRO1 remission at Week 52.

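### SAP Table AMAG.6.7 scores secondary PRO remission by a stricter rule than the protocol and SAP Table AMAG.4.1, and three related SAP lines carry copy or label errors

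*SAP*

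**What the plan says.** **PRO remission**

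- Protocol 9.1.2 gives the working definition, starting "PRO remission is defined as having an average daily AP score": AP at most 1 and SF at most 2.5, with no comparison to baseline.
- Protocol 10.3.3.2 lists the secondary endpoint, "To evaluate the efficacy of treatment with LY3074828 on PRO remission at Weeks 12 and 52", with the same two thresholds. The synopsis and Table AMAG.1 agree.
- SAP Table AMAG.4.1 repeats the two thresholds ("as superior to placebo in PRO remission (defined as SF" ≤2.5 and AP ≤1). SAP Section 4 says this table "shows the objectives and endpoints of the study as noted in the protocol".
- SAP Table AMAG.6.7 adds "and no worse than baseline at Week x". Its formula line applies the condition to SF and to AP separately. SAP 6.10.2 ("The secondary outcomes are stated in" Table AMAG.6.6) sends the reader to Tables AMAG.6.7 and AMAG.6.8 for derivation and analysis.
- Table AMAG.4.1 does print the condition for exploratory PRO1 remission ("and no worse than baseline) at Week 12"), but not for PRO remission.
- The SAP Version 2 revision history lists three changes. The one on endpoints reads "Added exploratory endpoints not specified in protocol based on data from new publications". None mentions PRO remission.

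**Lesser lines**

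- PRO1 remission (Table AMAG.6.7): the definition says SF ≤1.5. The formula below it says SF ≤2.5 and is labelled as PRO remission.
- Composite of endoscopic response and PRO remission: its Week 52 endpoint is written as both remissions in Tables AMAG.4.1 and AMAG.6.7.
- SAP 6.1.6.3 places the MMRM contrast with placebo at Week 12, Visit 8. The Schedule of Activities puts the Week 11-12 assessments at Visit 7.

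**The concern.** PRO remission at Week 12 is a secondary endpoint tested for superiority to placebo. The SAP carries two rules for it and does not say that one departs from the protocol. A derivation table may add detail, but a condition that changes who counts as a remitter changes the endpoint. A reader of the report who knows only the protocol would not expect the stricter rule, and could not tell when or why it was chosen. The rule also passes into every endpoint built on PRO remission, including both composites.

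The other three lines matter if followed literally. PRO1 remission would become the same endpoint as PRO remission. One Week 52 composite would duplicate the other. Four questionnaires would be compared at a visit where they are not collected.

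**Working it through.** **1. The plan's own figure.** The only stated power, 81%, is for endoscopic response (35% vs 15%, 60 per arm, two-sided 0.10). Null SE = √(2 × 0.25 × 0.75 / 60) = 0.0791; alternative SE = √((0.35 × 0.65 + 0.15 × 0.85) / 60) = 0.0769. Then z = (0.20 − 1.645 × 0.0791) / 0.0769 = 0.91, giving power 81.8%. It reproduces and does not depend on PRO remission.

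**2. Who is reclassified.** The rules differ when Week 12 SF ≤2.5 and AP ≤1, but one of them exceeds its baseline. That requires baseline SF <2.5 or baseline AP <1. Inclusion criterion 2 asks for SF ≥4 and/or AP ≥2, so such subjects can be eligible.

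| Baseline SF, AP | Week 12 SF, AP | Protocol and Table 4.1 | Table 6.7 |
|---|---|---|---|
| 6, 0.3 | 2, 0.9 | remission | no |
| 1, 2.5 | 2, 0.5 | remission | no |
| 6, 2.5 | 2, 0.9 | remission | remission |

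A reclassified subject who met entry has moved from AP ≥2 to ≤1, or from SF ≥4 to ≤2.5. A subject who met both entry criteria cannot be reclassified.

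**3. Size, under assumptions.** The documents give no SF or AP distribution. Assumed inputs were:

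- Baseline SF gamma, mean 4 or 6, SD 3; baseline AP normal clipped to 0–3, mean 1.8 or 2.0, SD 0.5 or 0.7; kept if entry was met.
- Week 12 value = baseline × normal factor (mean 0.55 or 0.85, SD 0.30 or 0.35, floored at 0) + noise (SF SD 0.5 or 1.0; AP SD 0.2 or 0.4), on a 1/7 grid.
- Change factor shared between SF and AP, or independent.

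That is 2⁷ × 2 = 256 scenarios, each with 200,000 draws before selection. Protocol rate minus SAP rate was 0.02 to 2.4 points, median 0.4. For an arm of 60 that is at most 60 × 0.0236 = 1.4 subjects. No subject meeting both entry criteria was reclassified. Outside the grid, with mean baseline SF 3, independent factors (mean 0.55, SD 0.35) and the larger noise values, the drop was 4.6 or 5.1 points, about 3 per 60. The grid is therefore not a bound.

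**4. Reach in Table AMAG.6.7.** PRO remission at Weeks 12 and 52 (2), its durability (1), PRO remission in PRO responders (1), the composite of remissions at Weeks 12 and 52 and its durability (3), and the response composite likewise (3): 2 + 1 + 1 + 3 + 3 = 10. Two are secondary and eight exploratory. Five are protocol endpoints: the two secondary ones and the three for the composite of remissions.

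**5. PRO1 formula.** A subject with SF 2.0 and AP 0.5, neither worse than baseline, fails the definition (≤1.5) but passes the formula (≤2.5). Everyone with SF above 1.5 and up to 2.5 who meets the other conditions is affected.

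**6. Week 52 response composite.** Reading a subscore as one variable in one segment (an assumption), these endoscopic responders are not in endoscopic remission and would be lost:

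- Ileal-colonic, baseline 14 (response ≤7): scores 4–7, or 2–3 with a subscore above 1.
- Ileal-colonic, baseline 7 (response ≤3): scores 2–3 with a subscore above 1.
- Isolated ileal, baseline 4 (response ≤2): score 2.

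**7. Visit label.** Visit 7 covers Days 78–85: (78 − 1)/7 = 11.0 to (85 − 1)/7 = 12.0 weeks. Visit 8 covers Days 86–92: 12.1 to 13.0 weeks. Seven visible measures have an MMRM (CDAI, PGRS, BMC, IBDQ, SF-36, FACIT-Fatigue, QIDS-SR16). The Schedule marks all seven at Visit 7 and none at Visit 8. For the last four there is no Visit 8 record. For CDAI, PGRS and BMC the documents disagree: there is no Visit 8 mark, yet the diary is daily and Table AMAG.6.7 has CDAI collected at each visit.

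**The case against.** The SAP does rank its texts. Section 4 says derivations follow later, and 6.10.2 points to Table AMAG.6.7, so a programmer would use that table. That stands: the problem is less which rule would be run than that the rule departs from the protocol unannounced.

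The revision history covers only Version 1 to Version 2, so the clause may date from Version 1. Protocol 10.3.1 and SAP 6.1 allow changes that are not principal features to be described in the CSR. Both points are fair, and neither can be checked from these documents. They do not explain why the SAP prints both rules.

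The inferential weight is modest. SAP Version 2 was approved before first unblinding, the clause applies alike to all arms, nothing is adjusted for multiplicity, and PRO remission is not powered. Only three of the ten endpoints are tested against placebo (Week 12 PRO remission and the two Week 12 composites); the other seven are descriptive. This stands and limits the severity.

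A per-arm drop is not a treatment effect. Pairing the 0.55 factor (active) with 0.85 (placebo) on the same grid, the treatment difference of about 15 to 25 points shrinks by 0.02 to 1.4 points (median 0.4). With mean baseline SF 3 it shrinks by about 2.4 to 2.8 points out of about 20. The counts per 60 fit only the 1000 mg and placebo arms; the other two arms have about 30 and half the count.

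The three lesser items are slips with correct wording nearby, and a careful programmer would probably resolve them. The Visit 8 label may come from Period 1 ending just before the Visit 8 dose.

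**Conclusion.** The point holds and should be fixed. The secondary endpoint PRO remission has two rules that classify some eligible subjects differently, and no passage marks the difference as a change. That rests on the text alone. The direction is also certain: the Table AMAG.6.7 rule can only remove remitters. The size is not known. Under the assumed distributions it is usually below 1 point and at most 2.4 points per arm, but about 5 points is possible if many subjects enter on abdominal pain with low stool frequency.

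The three lesser errors are real but of low severity, and the formula and composite errors concern exploratory endpoints. The primary endpoint, its alpha and its power are unaffected.

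**What to change.** 1. Use one PRO remission definition in the protocol, SAP Table AMAG.4.1 and Table AMAG.6.7. Either keep the protocol's two thresholds as the main analysis with the stricter rule as a sensitivity analysis, or keep the stricter rule and state and justify it in the SAP and CSR as a change from the protocol.
2. In the PRO1 cell of Table AMAG.6.7, change the formula to SF ≤1.5 and label it PRO1 remission.
3. In Tables AMAG.4.1 and AMAG.6.7, write the Week 52 endpoint of the response composite as endoscopic response together with PRO remission.
4. In SAP 6.1.6.3, change the label to Visit 7 (Week 11-12). For CDAI, PGRS and BMC, reconcile the Schedule of Activities with the SAP's collection timing.

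The cost is a few lines of SAP text and, at most, one extra analysis of data already collected. Keeping the protocol's definition needs no protocol amendment.
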